1. SUMMARY

Rationale: Hartmann's procedure was described for the first time in 1921 as an alternative to abdominoperineal resection for the treatment of upper rectal tumours. Hartmann's procedure is the surgical resection of the rectosigmoid colon with closure of the anorectal stump and formation of an end colostomy. Although Hartmann's procedure fell out of favour for rectal cancer after the introduction of restorative procedures, it remained the most common procedure in emergency setting for many years. Nowadays Hartmann's procedure is a useful procedure in selected cases e.g. severely ill patients with a high risk of anastomotic failure; However, restoring intestinal continuity for Hartmann patients is often associated with high morbidity, and about 70% will live with a permanent colostomy.

Hartmann procedure' is a rapid and simple surgical technique intended to decrease perioperative morbidity and mortality. This technique is often performed by young surgeons Indeed, end-colostomy may be necessary in situations where restoration of continuity is risky, either because of unfavourable local conditions (Hinchey IV peritonitis) or because a more definitive resection must be aborted due to hemodynamic instability.

In the last decade the Hartmann's procedure has been revalued in many studies.

In diverticular disease the results of DIVA arm of the LADIES trial (clinical trial on diverticulitis treatment) showed that more patients in the primary anastomosis group were stoma free compared with patients in the Hartmann's procedure group.

Other studies have observed no differences in major postoperative complications or postoperative mortality between patients undergoing primary anastomosis versus Hartmann's procedure.

Hartmann's procedure reversals were associated with a higher risk of serious postoperative complications than were stoma reversals after primary anastomosis with ileostomy.

The management of colorectal cancer emergencies is challenging. WSES guidelines recommend in case of perforation resection with anastomosis, with or without ileostomy. Hartmann's procedure should be preferred to simple colostomy, since colostomy appears to be associated with longer overall hospital stay and need for multiple operations, without a reduction in perioperative morbidity in patients with colorectal cancer obstruction. Resection with primary anastomosis

should be preferred for uncomplicated malignant left-sided large bowel obstruction in absence of other risk factors. Patients with high surgical risk are better managed with Hartmann's procedure

Despite the growing evidence in favour of primary anastomosis and its inclusion as a valid treatment option for perforated diverticulitis or perforated sigmoid colon in recent clinical practice guidelines, some surgeons have been hesitant to undertake anastomosis in the setting of purulent or faecal contamination and continue to choose Hartmann's procedure to eliminate concerns about anastomotic leakage.

Primary study objective:

GOODBYE HARTMANN – AFTER 100 YEARS HARTMANN'S PROCEDURE IS GOING TO BE ABANDONED?

STUDY PROTOCOL WITH ICF - VERSION 2 09.03.2021

1. To evaluate the role of Hartmann's procedure in emergency setting for left-sided colonic acute surgical disease (perforated diverticulitis with purulent or fecal peritonitis; colon cancer perforation-occlusion; ischemic colitis; abdominal trauma) and the type of surgery commonly performed in different level of care hospitals.
2. To investigate which factors contribute in the choice of Hartmann's procedure instead of colon resection with primary anastomosis (Hospital characteristics, surgeon experience, time of surgery, age of patients, comorbidities, etc)

Study design: International multicenter prospective cohort study.

Study population: Adult patients with left-sided colonic acute surgical disease who need surgery in an emergency setting (perforated diverticulitis with purulent or fecal peritonitis; colon cancer perforation-occlusion; ischemic colitis; abdominal trauma). All patients undergoing urgent surgery will be invited to participate and can choose to consent or decline

Primary outcome: Hartmann's procedure vs colonic resection with primary anastomosis performed in a 3-months interval in an emergency setting for left-sided acute surgical colonic diseases.

Secondary outcomes: risk factors for Hartmann procedure (Hospital characteristics (secondary, tertiary level, trauma center), surgeon experience, time of surgery (day of surgery- weekend; day or night), patient's age, comorbidities, clinical status etc.

Sample size calculation: The data will be used to investigate the specific characteristics to choose Hartmann's procedure versus primary anastomosis for left-sided acute surgical colonic diseases. Based on literature findings it has been estimated that, on average, three patients will undergo urgent left-sided colonic diseases resection per month at each participating centre. Applying root mean square percentage error (rMSPE) of 15%, 500 patients treated with left colon resection with or without primary anastomosis should be included.

Inclusion of 500 patients will be sufficient to analyze primary study objective 1 and primary study objective 2. Therefore, the aim is to include at least 500 patients.

2. INTRODUCTION AND RATIONALE

Left-sided surgical acute colonic diseases (perforated diverticulitis with generalized peritonitis, colon perforation, large bowel obstruction, colon cancer perforation or obstruction, ischemic colitis, abdominal trauma) are still a life-threatening condition requiring urgent surgical intervention.

Despite several published randomized trials, showing that primary anastomosis with or without protective ileostomy is feasible and randomized trials for laparoscopic lavage with conflicting results, the Hartmann's procedure, described for the first time in 1921 as an alternative to abdominoperineal resection for the treatment of upper rectal tumours, is still performed in many hospitals worldwide. Hartmann's procedure is the surgical resection of the rectosigmoid colon with closure of the anorectal stump and formation of an end colostomy. It remained the most common procedure for acute diverticulitis and colonic perforation in emergency setting for many years. Hartmann's procedure is safe for severely ill patients; however,

GOODBYE HARTMANN – AFTER 100 YEARS HARTMANN'S PROCEDURE IS GOING TO BE ABANDONED?

STUDY PROTOCOL WITH ICF - VERSION 2 09.03.2021

restoring intestinal continuity for such patients is often associated with high morbidity leaving a great percentage of patients with (up to 50%) with a permanent stoma. [1]

Hartmann procedure' is a rapid and simple surgical technique intended to decrease perioperative morbidity and mortality. This technique is often performed by young surgeons. Indeed, end-colostomy may be necessary in situations where restoration of continuity is risky, either because of unfavourable local conditions (Hinchey IV peritonitis) or because a more definitive resection must be aborted due to hemodynamic instability. Although anastomosis at the time of surgery is an alternative approach to Hartmann's procedure, there have been concerns about the safety of this approach.

In the last decade the Hartmann's procedure has been revalued and the results of different studies [DIVA arm of the LADIES trial (the fourth and largest randomized clinical trial to date to compare Hartmann's procedure with primary resection and anastomosis in patients with perforated diverticulitis with purulent or and fecal peritonitis); DIVERTI study; Halim et Al] showed that more patients in the primary anastomosis group were stoma free compared with patients in the Hartmann's procedure group. [2,3,4]

Several studies have observed no differences in major postoperative complications or postoperative mortality between patients undergoing primary anastomosis versus Hartmann's procedure. Hartmann's procedure reversals were associated with a higher risk of serious postoperative complications than were stoma reversals after protected primary anastomosis. [2-7]

The management of colorectal cancer emergencies is challenging. WSES guidelines recommend in case of perforation resection with anastomosis, with or without ileostomy. Hartmann's procedure should be preferred to simple colostomy, since colostomy appears to be associated with longer overall hospital stay and need for multiple operations, without a reduction in perioperative morbidity in patients with colorectal cancer obstruction. Resection with primary anastomosis should be preferred for uncomplicated malignant left-sided large bowel obstruction in absence of other risk factors. Patients with high surgical risk are better managed with Hartmann's procedure. Despite the growing evidence in favour of primary anastomosis and its inclusion as a valid treatment option for perforated diverticulitis or perforated sigmoid colon cancer in recent clinical practice guidelines, surgeons have been reluctant to perform anastomosis. Moreover, the postoperative course of the septic patient is unpredictable and it very hard to estimate it intraoperatively.

In the setting of purulent or fecal contamination most surgeons choose Hartmann's procedure to eliminate also legal concerns about anastomotic leakage. It's important to note that most of these procedures are performed off normal working hours when maybe best colorectal expertise is lacking for decision making regarding anastomosis. [8-10]

3. STUDY OBJECTIVES

- To evaluate the role of Hartmann's procedure in emergency setting for left-sided colonic acute surgical disease (perforated diverticulitis with purulent or fecal peritonitis; colon cancer perforation-occlusion; ischemic colitis; abdominal trauma) and the type of surgery commonly performed in different level of care hospitals.
- To investigate which factors contribute in the choice of Hartmann's procedure instead of colon resection with primary anastomosis (Hospital characteristics, surgeon experience, time of surgery, age of patients, comorbidities, etc)

GOODBYE HARTMANN – AFTER 100 YEARS HARTMANN’S PROCEDURE IS GOING TO BE ABANDONED?

STUDY PROTOCOL WITH ICF - VERSION 2 09.03.2021

- To evaluate postoperative course and complications rate (Length of stay, complication, reoperation) of different surgical procedures.

4. STUDY DESIGN

4.1 STUDY TYPE

International multicenter prospective cohort study.

4.2 DURATION OF THE STUDY

Data from 3 months cohort of patients who underwent urgent or emergency Hartmann’s procedure, resection with primary anastomosis for left-sided colonic disease from March 1st 2021 until May 31st 2021 will be recorded with one-year follow-up from surgery until May 2022. The total study duration will be from January 2021 until December 2022(22 months).

4.3 STUDY TIMELINE

- November 1st – November 30th 2020: Database building and approval of the first version of the protocol.
- December 2020: Invitation of surgeons by sending first version of protocol and CRF.
- January 2021: study document preparation. Protocol and CRF refinement based on comments of pilot study results.
- February 2021:: Final protocol and CRF is sent to participating centers. All participating surgeons receive a REDCap database login.
- March 2021 – May 2021: Data collection.
- March 2022 – May 2022: Follow-up
- June 2022 – December 2022: Analysis and manuscript writing.

4.4 STUDY SETTING

This study will be performed in a multicenter and international setting. A large proportion of the group of hospitals that comprises Emergency Surgery Unit is expected to participate.

5. STUDY POPULATION

5.1 POPULATION

All patients undergoing urgent surgery for left-sided colonic disease will be invited to participate and can choose to consent or decline between March -May 2021.

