5.5 PRIMARY OUTCOME PARAMETER

- Number of Hartmann's procedure vs colic resection with primary anastomosis performed in 3-months in urgent or emergency setting for left-sided acute colonic diseases.

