5.8 PATIENT CHARACTERISTICS

- Age
- Sex
- Weight
- Previous abdominal surgery
- Charlson comorbidity index
- ASA classification
- Clinical status: stable patient; unstable patient; sepsis (qSOFA score)

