8.3 DATA COLLECTION AND DATA ENTERING

All patient data will be entered anonymously by or under supervision of the treating physician(s). Only anonymised data will be uploaded to the database. No patient identifiable data will be collected. Data collected will be on comorbidities, treatment/operation. No dates (e.g. date of surgery) will be collected. The study will be carried out in accordance with national and international guidelines, as well as the basic principles of the protection of the rights and dignity of Human Beings, as set out in the Helsinki Declaration (64th Assembly Fortaleza, Brazil, in October 2013), and according to current legislation.

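### The primary outcome counts operations performed, but entry depends on consent and no tally of eligible operations is described, so non-participation lowers the count and may bias the Hartmann's share

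*Protocol*

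**What the plan says.** Section 5.5 of the Protocol gives the primary outcome as "Number of Hartmann's procedure vs colic resection with primary anastomosis performed in 3-months in urgent or emergency setting". This is a count of operations, and the ratio of the two counts carries the answer to the first objective.

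Entry is at the level of the patient. Section 5.1 says that patients having urgent left-sided colonic surgery "will be invited to participate and can choose to consent or decline between March -May 2021", and the Summary repeats the rule: "All patients undergoing urgent surgery will be invited to participate and can choose to consent or decline".

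The Protocol also ties procedure to severity. The opening of the Summary presents Hartmann's as useful in selected, severely ill patients in whom an anastomosis is likely to fail. Later in the Summary, and again in section 2, in the discussion of colorectal cancer emergencies, it states: "Patients with high surgical risk are better managed with Hartmann's procedure". Section 5.8 records whether patients are stable, unstable or septic, so very ill patients belong to the cohort. Section 5.3 excludes one part of that group, unstable patients who had damage control procedures.

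Sections 4 to 8 describe no screening log, no count of eligible or declining patients by procedure, and no comparison of participants with non-participants. Section 6.1 does not mention non-participation.

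**The concern.** The outcome names all operations of the two types in the window. The data source appears to be the subset whose patients agreed to take part. Two consequences follow, and they need different conditions.

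- **The count.** Any refusal or inability to consent lowers the number of procedures recorded, whether or not consent is related to procedure.
- **The share.** The Hartmann's proportion is distorted only if consent differs between the two procedures. A plausible route is severity. In emergency surgery for peritonitis, patients who are septic or sedated may be harder to enrol, and the Protocol associates the sicker patients with Hartmann's. The observed share would then be too low, and the severe end of the case mix would be thinned in the analysis of what drives the choice of operation.

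The study asks in its title whether Hartmann's is going to be abandoned. An error in this direction would lean towards yes, and enrolling more patients would not reduce it. This is a matter of data capture: a later analysis plan cannot recover a denominator by procedure that no centre recorded.

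**Working it through.** The Protocol gives no consent rate, no expected Hartmann's share and no participation figure, so it has no figure of its own to reproduce here. Only the target of 500 patients (section 5.4) comes from the document. All shares and consent rates below are assumptions.

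**1. Count.** If a fraction c of eligible patients consents, the recorded number is c times the true number. With c = 0.70 for both procedures, 70% of the Hartmann's operations are recorded, and the share is unchanged.

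**2. Share.** Let p be the true Hartmann's share, and cH and cA the consent rates for Hartmann's and anastomosis.

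Observed share = p·cH / [p·cH + (1 − p)·cA]

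With p = 0.60:

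| cH / cA | Calculation | Observed | Bias (points) |
|---|---|---|---|
| 0.90 / 0.95 | 0.540 / (0.540 + 0.380) | 58.7% | −1.3 |
| 0.80 / 0.95 | 0.480 / (0.480 + 0.380) | 55.8% | −4.2 |
| 0.70 / 0.95 | 0.420 / (0.420 + 0.380) | 52.5% | −7.5 |
| equal rates | the common factor cancels | 60.0% | 0 |

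**3. Yardstick.** The 95% half-width at N = 500 is 1.96·√(0.60·0.40/500) = 1.96·0.0219 = 0.043, or 4.3 points. For true shares of 30%, 50% and 70%, a consent ratio cH/cA of about 0.82 to 0.84 produces a bias equal to the half-width (4.0 to 4.4 points).

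**4. Other true shares.** Fix cA at 0.90 and let cH fall from 0.90 to 0.50. The bias runs from 0 to −10.8 points at p = 0.30, from 0 to −14.3 at p = 0.50, and from 0 to −13.5 at p = 0.70. The far ends need a very large gap in consent.

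**5. Consent driven by severity alone.** Let s be the fraction very ill, hS and hN the Hartmann's share in the very ill and the others, and cS and cN their consent rates.

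True share = s·hS + (1 − s)·hN

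Observed share = [s·cS·hS + (1 − s)·cN·hN] / [s·cS + (1 − s)·cN]

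Example: s = 0.30, hS = 0.80, hN = 0.40, cS = 0.60, cN = 0.90.

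- True: 0.24 + 0.28 = 52.0%.
- Observed: (0.144 + 0.252) / (0.180 + 0.630) = 0.396 / 0.810 = 48.9%.
- Bias: −3.1 points.

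Over s = 0.20 to 0.40, hS = 0.70 to 0.80, hN = 0.40, cS = 0.40 to 0.80 and cN = 0.90, the bias runs from −0.5 to −6.9 points. It is zero if the Hartmann's share does not depend on severity.

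**The case against.** Several points on the other side are fair.

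- **Leaving out decliners is not stated.** Consent is not among the inclusion criteria in 5.2, refusal is not an exclusion in 5.3, and 4.2 describes the cohort by the operation undergone. Omission of those who decline is the natural reading of 5.1, but it remains a reading.
- **The consent pages and the CRF are not available.** Proxy or deferred consent may be described there, and would narrow the gap between very ill and other patients. It would not by itself supply a count of those who did not take part.
- **Part of the sickest group is outside the target population.** The damage control exclusion in 5.3 removes some of the patients least able to consent. This reduces the problem, but unstable and septic patients still appear in 5.8.
- **Loss through early death is not clearly related to procedure.** The Summary and section 2 cite studies that found no difference in postoperative mortality between the two operations. That evidence comes from other cohorts and does not settle the matter, but it weakens this route.
- **The size is assumed.** The mildest scenario, 1.3 points, lies well inside the sampling half-width.

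A reader might infer that the bias certainly runs against Hartmann's. The document does not support that: it gives no consent rates, and equal consent leaves the share intact. A reader might also infer that the gap could never be noticed. That is too strong, because section 5.7 collects each hospital's annual volume of left-sided colonic disease, which allows a rough check on capture by centre. Since the Protocol does not describe that volume as split by procedure, it cannot correct the share.

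**Conclusion.** The concern holds in conditional form. The outcome in 5.5 and the entry rule in 5.1 do not describe the same set of operations, and the available text provides no means of measuring the difference by procedure. Undercounting follows from any non-participation, provided decliners are not recorded. A downward bias in the Hartmann's share needs two further links: severity related to procedure, which the Protocol supports, and consent related to severity, which is plausible but assumed.

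Under the assumptions shown, the bias is 1.3 to 7.5 points at a true share of 60%, and 0.5 to 6.9 points when severity alone drives consent, against a half-width of 4.3 points at 500 patients. The problem may therefore be negligible or may exceed the sampling error, and the plan as written cannot tell which. That justifies a small change to data capture. It does not show that the study's result will be wrong.

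**What to change.** In section 5.1, require each centre to report one anonymous aggregate tally for its enrolment window: eligible operations by procedure (Hartmann's, resection with primary anastomosis, other), and within each the numbers consented, declined and unable to consent.

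In section 5.5, state that participation will be reported by procedure, and that the Hartmann's share will be given among all eligible operations alongside the share in the consented cohort. Keep the model of factors behind the choice of operation on consented patients, for whom individual data exist.

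The tally holds no patient-level data on non-participants, so it is compatible with sections 8.3 and 8.4. The cost is modest site effort and a small ethics amendment across the participating centres. Version 2 is dated 9 March 2021, after the window in 4.2 opened on 1 March, so centres may have to reconstruct the first days from local records. Eligibility in an aggregate tally cannot be verified centrally, which is why the two shares should stand side by side and the tally should not replace the cohort figure.

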5.2 INCLUSION CRITERIA

In order to be eligible to participate in this study, a subject must meet all of the following criteria:

- Aged 18 years or older;

GOODBYE HARTMANN – AFTER 100 YEARS HARTMANN'S PROCEDURE IS GOING TO BE ABANDONED?

STUDY PROTOCOL WITH ICF - VERSION 2 09.03.2021

- Patients admitted in Emergency setting for left-sided colonic disease (perforated diverticulitis with purulent or fecal peritonitis; large bowel perforation-obstruction; colon cancer perforation-obstruction; ischemic colitis; abdominal trauma).
- Patients who underwent urgent or emergency surgery for left-sided colonic disease (perforated diverticulitis with purulent or fecal peritonitis; large bowel perforation- obstruction; colon cancer perforation-obstruction; ischemic colitis; abdominal trauma).

5.3 EXCLUSION CRITERIA

- Aged 17 or younger.
- Elective surgery.
- Non-surgical treatment.
- Patients with personal history of colorectal cancer treated surgically.
- Patients with stoma.
- Unstable patients who benefited of damage control procedures.

5.4 SAMPLE SIZE CALCULATION

The data will be used to investigate the specific characteristics to choose Hartmann's procedure versus primary anastomosis for left-sided acute surgical colonic diseases. Based on literature findings it has been estimated that, on average, three patients will undergo urgent left-sided colonic diseases resection per month at each participating centre. Applying root mean square percentage error (rMSPE) of 15%, 500 patients treated with left colon resection with or without primary anastomosis should be included.

Inclusion of 500 patients will be sufficient to analyze primary study objective 1 and primary study objective 2. Therefore, the aim is to include at least 500 patients.

METHODS

5.5 PRIMARY OUTCOME PARAMETER

- Number of Hartmann's procedure vs colic resection with primary anastomosis performed in 3-months in urgent or emergency setting for left-sided acute colonic diseases.

5.6 SECONDARY OUTCOME PARAMETERS

- Patient characteristics
- Etiology
- Hospital characteristics
- Treatment
- Surgeon experience
- Time of surgery
- Follow-up

5.7 LIST OF STUDY PARAMETERS

- Etiology: perforated diverticulitis; perforated colonic cancer; large bowel perforation-obstruction; colon cancer perforation-obstruction; colon ischemia; abdominal trauma.
- Hospital Characteristics: hospital type (academic, non-academic teaching, categorical, secondary hospital, tertiary hospital, level 4- trauma center); annual volume of

GOODBYE HARTMANN – AFTER 100 YEARS HARTMANN'S PROCEDURE IS GOING TO BE ABANDONED?

STUDY PROTOCOL WITH ICF - VERSION 2 09.03.2021

emergency surgical procedures; annual volume of left-sided colonic disease; types of diagnostic and treatment modalities that are available in the hospital.

- Treatment: Hartmann's procedure, colonic resection with primary anastomosis with or without diverting stoma, stoma without colic resection.
- Surgeon experience (surgeon in training: less than 50 colorectal resections performed; less than 5 resections per year in the last 5 years; Trained surgeon: more than 50 colorectal resections performed; more than 10 resections per year in the last 5 years)
- Time of surgery: weekdays, weekend, public holidays, night shift (day: 8am- 8pm; night: 8pm-8am)
- Postoperative course: Clavien-Dindo Classification; reoperation
- Follow-up: to evaluate the number of patients treated with Hartmann's procedure have a permanent stoma after one year.

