6. ANALYSIS

6.1 ANALYSIS STRATEGY

The first study objective is to investigate what factors contribute in the choice of Hartmann's procedure instead of colonic resection with primary anastomosis and what type of surgery is commonly performed in different level of care hospitals

Univariate analysis is performed on relevant parameters that are described in chapter 5.7- list of study parameters and 5.8-patient characteristics. Factors that are considered to be clinically relevant based on literature and/or expert opinion are selected for multivariate analysis.

Backwards selection is used to exclude values of $p > 0.05$ from the model.

The results obtained by the described analyses will also be performed in subgroups of patients who underwent Hartmann's procedure or primary anastomosis with or without diverting ileostomy. By performing this sensitivity analysis, we will investigate the factors behind the choice to perform Hartmann's procedure or colic resection with primary anastomosis.

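### Country is not among the factors that feed the analysis, so associations of hospital level and surgeon experience with Hartmann's procedure may reflect national practice

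*Protocol*

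**What the plan says.** The Protocol describes an international cohort in the Summary and in Sections 4.1 and 4.4: "This study will be performed in a multicenter and international setting".

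The first objective in the Summary includes "the type of surgery commonly performed in different level of care hospitals". The second reads "To investigate which factors contribute in the choice of Hartmann's procedure instead of colon resection with primary anastomosis (Hospital characteristics, surgeon experience, time of surgery", followed by patient factors.

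Section 6.1 says where the candidate factors come from: "Univariate analysis is performed on relevant parameters that are described in chapter 5.7- list of study parameters and 5.8-patient characteristics". Section 5.7 opens its hospital entry with "Hospital Characteristics: hospital type (academic, non-academic teaching, categorical, secondary hospital, tertiary hospital, level 4- trauma center" and adds two annual volumes and the available diagnostic and treatment modalities. The surgeon entry starts "Surgeon experience (surgeon in training: less than 50 colorectal resections performed" and is defined by numbers of resections. Section 5.8 lists patient variables only. Country, region and centre are in neither list.

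For the multivariable step, Section 6.1 says "Factors that are considered to be clinically relevant based on literature and/or expert opinion are selected for multivariate analysis" and then "Backwards selection is used to exclude values of $p > 0.05$ from the model". It exempts no factor from that removal rule and states no stratification or adjustment by country or centre.

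**The concern.** Hospital level is a property of the centre, so its association with the choice of procedure is estimated by comparing centres, and in an international study many of those comparisons cross borders. If Hartmann's procedure is used more in some countries, and those countries also contribute more hospitals of one level, the national difference shows up as an apparent effect of hospital level. The same can happen with volume, available modalities and surgeon experience.

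A centre random effect or a cluster-robust standard error would not remove this. Either one corrects the uncertainty, but the bias lies in the comparison between centres.

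At stake are the hospital and surgeon findings of objective 2, and any reading of the level-of-care comparison in objective 1 that goes beyond description. A difference in national practice could be published as a reason related to hospital level.

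**Working it through.** **Inputs from the Protocol.** The target is 500 patients, at three per centre per month (Section 5.4), over three months (Section 4.2). That implies 500 / (3 × 3) = 55.6, so 56 centres of about 9 patients. The Protocol gives no figure for between-country variation, so there is no stated value to reproduce. Everything below is assumption.

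**Closed-form illustration.** Assume two country groups of equal size, A and B, and no effect of hospital level within either. Let h be the Hartmann's share and s the share of patients in secondary hospitals, the rest being in tertiary hospitals. Pooling the two groups:

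- secondary, Hartmann's: a = sA·hA + sB·hB
- secondary, anastomosis: b = sA(1−hA) + sB(1−hB)
- tertiary, Hartmann's: c = (1−sA)hA + (1−sB)hB
- tertiary, anastomosis: d = (1−sA)(1−hA) + (1−sB)(1−hB)
- crude OR = ad / (bc). The true OR within each country group is 1.

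For h = 40% vs 65% and s = 30% vs 60%:

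- a = 0.12 + 0.39 = 0.51
- b = 0.18 + 0.21 = 0.39
- c = 0.28 + 0.26 = 0.54
- d = 0.42 + 0.14 = 0.56
- OR = (0.51 × 0.56) / (0.39 × 0.54) = 0.2856 / 0.2106 = 1.36

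| Hartmann's share, A vs B | Secondary share, A vs B | ad / bc | Spurious OR |
|---|---|---|---|
| 40% vs 65% | 45% vs 45% | equal | 1.00 |
| 45% vs 55% | 40% vs 50% | 0.2525 / 0.2425 | 1.04 |
| 45% vs 60% | 30% vs 60% | 0.2698 / 0.2248 | 1.20 |
| 40% vs 65% | 30% vs 60% | 0.2856 / 0.2106 | 1.36 |
| 35% vs 70% | 20% vs 70% | 0.3416 / 0.1666 | 2.05 |
| 40% vs 65% | 60% vs 30% | 0.2110 / 0.2860 | 0.74 |

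The first row shows that a large gap in national practice alone does no harm. The last row shows that the sign can go either way.

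**How often a null effect would look significant.** The simulation used 56 centres of 9 patients, a between-centre SD of 0.4 on the logit scale, an exchangeable GEE so that clustering is handled, and 300 to 400 replicates per run. Without country, p < 0.05 arose in about 5% of runs at OR 1.00, 6% at 1.04, 13–16% at 1.20, 24–28% at 1.36 and 76–85% at 2.05. The ranges are the spread over repeated runs. With country in the model, in the three scenarios from OR 1.20 to 2.05, rejection was about 3–7% and the OR about 1.0.

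**A second set of assumptions.** This one used ten countries, a 50% Hartmann's share, a between-centre SD of 0 or 0.3, ordinary logistic regression and a true OR of 1. National practice and hospital mix were correlated at 0.5 to 0.8.

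| Country SD (logit) | Average OR without country | Rejection at 5% |
|---|---|---|
| 0.3 | 1.1–1.2 | 13–24% |
| 0.5 | 1.2–1.4 | 24–41% |
| 0.8 | 1.3–1.6 | 37–62% |

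With country in the model the OR was 0.97–1.02 and rejection 3–11%. With zero correlation the OR without country was about 1.0, yet rejection still reached 7–28%. That excess comes from ignored clustering, so the rejection rates in this table are not all due to confounding.

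**The case against.** - **A reader might infer that the effects are confounded.** The documents do not show that. Confounding needs national practice to differ and the hospital or surgeon mix to differ with it, and the Protocol has data on neither. Section 2 mentions legal worries about leakage and thinner expertise outside working hours, but it does not say that these vary between countries. The second is at least partly covered by time of surgery and surgeon experience in 5.7. This objection stands, so the point is one of risk.
- **A reader might extend the point to both primary objectives in full.** The count of Hartmann's procedures against primary anastomosis (Section 5.5) is descriptive and needs no adjustment. A plain description of what is done at each level of care needs none either. This stands too. No calculation was made for surgeon experience, and the argument carries over to it only by analogy.
- **The Protocol does not bar country.** Multivariable factors are chosen on literature or expert opinion, and a statistical analysis plan could add country. That is true. But Section 6.1 names its source lists and its removal rule, and country is in neither list and protected by no rule.
- **A reader might infer that country will not be collected.** That does not follow. Sites have their own database logins and data are held by centre (Sections 8.1 and 8.4), so country should be derivable. The case report form in appendix 1 is not shown. The gap is in the analysis parameters, and it is not shown to be in the data.

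**Conclusion.** The point holds as a risk. Because Sections 5.7, 5.8 and 6.1 leave out country, region and centre, the associations of hospital level, other hospital characteristics and surgeon experience with the choice of Hartmann's procedure may be confounded by national practice. This touches objective 2 and any inferential reading of the level-of-care comparison in objective 1. It leaves the overall Hartmann's proportion untouched.

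The size is unknown. Under the two-group assumptions above, the spurious OR runs from 1.0 to about 2.05, or below 1 (0.74 in the example) if the mix is reversed. The larger values need gaps of 25 to 35 percentage points in Hartmann's use together with gaps of 30 to 50 points in hospital mix. Modest gaps of 10 points in each give 1.04.

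**What to change.** 1. In Section 5.7, add country to the hospital characteristics, derived from the participating site.
2. In Section 6.1, keep country in the multivariable model regardless of the p > 0.05 backward-selection rule. Without that exemption the term could be added and then dropped. Where countries have few centres, use region, with the grouping fixed before the outcome data are examined.
3. Show the Hartmann's share by level of care within region, so that readers can see whether a level-of-care difference persists within regions.

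No new patient data should be needed. The cost is a few degrees of freedom and somewhat wider intervals for hospital factors where level and country overlap.
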